### **Appendix III**

#### **Immune related adverse event management algorithms**

These general guidelines constitute guidance to the Investigator. The guidance applies to all immuno-oncology (I-O) agents and regimens. A general principle is that differential diagnoses should be diligently evaluated according to standard medical practice. Non-inflammatory etiologies should be considered and appropriately treated. Corticosteroids are a primary therapy for immuno-oncology drug-related adverse events. The oral equivalent of the recommended IV doses may be considered for ambulatory patients with low-grade toxicity. The lower bioavailability of oral corticosteroids should be taken into account when switching to the equivalent dose of oral corticosteroids. Consultation with a medical or surgical specialist, especially prior to an invasive diagnostic or therapeutic procedure, is recommended. The frequency and severity of the related adverse events covered by these algorithms will depend on the immuno-oncology agent or regimen being used.

## GI Adverse Event Management Algorithm

Rule out non-inflammatory causes. If non-inflammatory cause is identified, treat accordingly and continue I-O therapy. Opiates/narcotics may mask symptoms of perforation. Infliximab should not be used in cases of perforation or sepsis.

[figure not shown]

Patients on IV steroids may be switched to an equivalent dose of oral corticosteroids (e.g. prednisone) at start of tapering or earlier, once sustained clinical improvement is observed. Lower bioavailability of oral corticosteroids should be taken into account when switching to the equivalent dose of oral corticosteroids.

# Renal Adverse Event Management Algorithm

[figure not shown]
Rule out non-inflammatory causes. If non-inflammatory cause, treat accordingly and continue I-O therapy

Patients on IV steroids may be switched to an equivalent dose of oral corticosteroids (e.g. prednisone) at start of tapering or earlier, once sustained clinical improvement is observed. Lower bioavailability of oral corticosteroids should be taken into account when switching to the equivalent dose of oral corticosteroids.

# Pulmonary Adverse Event Management Algorithm

[figure not shown]
Rule out non-inflammatory causes. If non-inflammatory cause, treat accordingly and continue I-O therapy. Evaluate with imaging and pulmonary consultation.

Patients on IV steroids may be switched to an equivalent dose of oral corticosteroids (e.g. prednisone) at start of tapering or earlier, once sustained clinical improvement is observed. Lower bioavailability of oral corticosteroids should be taken into account when switching to the equivalent dose of oral corticosteroids.

# Hepatic Adverse Event Management Algorithm

Rule out non-inflammatory causes. If non-inflammatory cause, treat accordingly and continue I-O therapy. Consider imaging for obstruction.

[figure not shown]
Patients on IV steroids may be switched to an equivalent dose of oral corticosteroids (e.g. prednisone) at start of tapering or earlier, once sustained clinical improvement is observed. Lower bioavailability of oral corticosteroids should be taken into account when switching to the equivalent dose of oral corticosteroids.

\*I-O therapy may be delayed rather than discontinued if AST/ALT ≤ 8 x ULN and T.bili ≤ 5 x ULN.

\*\*The recommended starting dose for grade 4 hepatitis is 2 mg/kg/day methylprednisolone IV.

# Endocrinopathy Management Algorithm

[figure not shown]
Rule out non-inflammatory causes. If non-inflammatory cause, treat accordingly and continue I-O therapy. Consider visual field testing, endocrinology consultation, and imaging.

Patients on IV steroids may be switched to an equivalent dose of oral corticosteroids (e.g. prednisone) at start of tapering or earlier, once sustained clinical improvement is observed. Lower bioavailability of oral corticosteroids should be taken into account when switching to the equivalent dose of oral corticosteroids.

# Skin Adverse Event Management Algorithm

Rule out non-inflammatory causes. If non-inflammatory cause, treat accordingly and continue I-O therapy.

[figure not shown]

Patients on IV steroids may be switched to an equivalent dose of oral corticosteroids (e.g. prednisone) at start of tapering or earlier, once sustained clinical improvement is observed. Lower bioavailability of oral corticosteroids should be taken into account when switching to the equivalent dose of oral corticosteroids.

\*Refer to NCI CTCAE v4 for term-specific grading criteria.

# Neurological Adverse Event Management Algorithm

Rule out non-inflammatory causes. If non-inflammatory cause, treat accordingly and continue I-O therapy.

Patients on IV steroids may be switched to an equivalent dose of oral corticosteroids (e.g. prednisone) at start of tapering or earlier, once sustained clinical improvement is observed. Lower bioavailability of oral corticosteroids should be taken into account when switching to the equivalent dose of oral corticosteroids.

## **Appendix IV**

### **A) RECIST Criteria:**

#### **Measurable Disease**

Measurable lesions are defined as those that can be accurately measured in at least one dimension (longest diameter to be recorded) as  $\geq 20$  mm with conventional techniques (CT, MRI, x-ray) or as  $\geq 10$  mm with spiral CT scan. All tumor measurements must be recorded in millimeters (or decimal fractions of centimeters).

#### **Non-measurable Disease**

All other lesions (or sites of disease), including small lesions (longest diameter  $< 20$  mm with conventional techniques or  $< 10$  mm using spiral CT scan), are considered non-measurable disease. Bone lesions, CNS metastases, leptomeningeal disease, ascites, pleural/pericardial effusions, lymphangitis cutis/pulmonis, inflammatory breast disease, abdominal masses (not followed by CT or MRI), and cystic lesions are all non-measurable.

#### **Target Lesions**

All measurable lesions up to a maximum of five lesions per organ and 10 lesions in total, representative of all involved organs, should be identified as target lesions and recorded and measured at baseline. Target lesions should be selected on the basis of their size (lesions with the longest diameter) and their suitability for accurate repeated measurements (either by imaging techniques or clinically). A sum of the longest diameter (LD) for all target lesions will be calculated and reported as the baseline sum LD. The baseline sum LD will be used as reference by which to characterize the objective tumor response.

#### **Non-target Lesions**

All other lesions (or sites of disease) should be identified as non-target lesions and should also be recorded at baseline. Non-target lesions include measurable lesions that exceed the maximum numbers per organ or total of all involved organs as well as non-measurable lesions. Measurements of these lesions are not required but the presence or absence of each should be noted throughout follow-up.

#### **Guidelines for Evaluation of Measurable Disease**

All measurements should be taken and recorded in metric notation using a ruler or calipers. All baseline evaluations should be performed as closely as possible to the beginning of treatment and never more than 4 weeks before the beginning of the treatment.

Note: Tumor lesions that are situated in a previously irradiated area might or might not be considered measurable.

The same method of assessment and the same technique should be used to characterize each identified and reported lesion at baseline and during follow-up. Imaging-based evaluation is preferred to evaluation by clinical examination when both methods have been used to assess the antitumor effect of a treatment.

### **Clinical lesions**

Clinical lesions will only be considered measurable when they are superficial (e.g., skin nodules and palpable lymph nodes). In the case of skin lesions, documentation by color photography, including a ruler to estimate the size of the lesion, is recommended.

### **Chest x-ray**

Lesions on chest x-ray are acceptable as measurable lesions when they are clearly defined and surrounded by aerated lung. However, CT is preferable.

### **Conventional CT and MRI**

These techniques should be performed with cuts of 10 mm or less in slice thickness contiguously. Spiral CT should be performed using a 5 mm contiguous reconstruction algorithm. This applies to tumors of the chest, abdomen, and pelvis. Head and neck tumors and those of extremities usually require specific protocols.

### **Ultrasound (US)**

When the primary endpoint of the study is objective response evaluation, US should not be used to measure tumor lesions. It is, however, a possible alternative to clinical measurements of superficial palpable lymph nodes, subcutaneous lesions, and thyroid nodules. US might also be useful to confirm the complete disappearance of superficial lesions usually assessed by clinical examination.

### **Endoscopy and Laparoscopy**

The utilization of these techniques for objective tumor evaluation has not yet been fully and widely validated. Their uses in this specific context require sophisticated equipment and a high level of expertise that may only be available in some centers. Therefore, the utilization of such techniques for objective tumor response should be restricted to validation purposes in reference centers. However, such techniques can be useful to confirm complete pathological response when biopsies are obtained.

### **Tumor markers**

n/a

### **Cytology and Histology**

These techniques can be used to differentiate between partial responses (PR) and complete responses (CR) in rare cases (e.g., residual lesions in tumor types such as germ cell tumors, where known residual benign tumors can remain).

### **Response Criteria**

#### **Evaluation of Target Lesions**

Complete Response (CR): Disappearance of all target lesions

Partial Response (PR): At least a 30% decrease in the sum of the longest diameter (LD) of target lesions, taking as reference the baseline sum LD

Progressive Disease (PD): At least a 20% increase in the sum of the LD of target lesions, taking as reference the smallest sum LD recorded from the time treatment was started or from the time treatment was held or the appearance of one or more new lesions

Stable Disease (SD): Neither sufficient shrinkage to qualify for PR nor sufficient increase to qualify for PD, taking as reference the smallest sum LD since the treatment was started or held.

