  - Dosing delays or interruptions to allow for prolonged steroid tapers to manage drug-related adverse events are allowed. Prior to re-initiating treatment in a subject with a dosing interruption lasting > 6 weeks, the Investigator must be consulted. Tumor assessments should continue as per protocol even if dosing is interrupted or delayed
  - Dosing interruptions or delays lasting > 6 weeks that occur for non-drug-related reasons may be allowed if approved by the Investigator. Prior to re-initiating treatment in a subject with a dosing interruption lasting > 6 weeks, the Investigator must be consulted. Tumor assessments should continue as per protocol even if dosing is interrupted
- Any adverse event, laboratory abnormality, or intercurrent illness which, in the judgment of the Investigator, presents a substantial clinical risk to the subject with continued nivolumab dosing
  - Treatment beyond radiographic progression is allowed if it is felt by the investigators that there is clinical benefit. If new or pre-existing asymptomatic brain lesions are noted on surveillance MRI. These patients need to be followed closely with follow up brain imaging on treatment and can receive gamma knife therapy while actively receiving therapy on study – study drugs do not require disruption while receiving gamma knife therapy unless clinically indicated to do so. Use of steroids after Gamma knife therapy should be minimized but can be used per clinical discretion of the treating radiation oncologist.

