## 12.0 MEASUREMENT OF EFFECT

### 12.1 Primary End Point

***Objective response:*** Objective response (OR) is the primary endpoint of this trial, subjects with measurable disease will be assessed by standard criteria. For the purposes of this study, subjects should be re-evaluated with CT scan with contrast (if clinically indicated

non-contrast CT or PET/CT could be used in lieu of CT with contrast) every 8 of weeks i.e after every 2 cycles (4 treatments) of Nivolumab.

Evaluation of response: Response and progression will be evaluated in this study using the Response Evaluation Criteria in Solid Tumors (RECIST) guideline (version 1.1). For the purpose of this study treatment will be discontinued in patients who experience disease progression by RECIST v1.1 (see Appendix IVa) with the following caveat: since it is known that there can be initial progression by RECIST v1.1 criteria with immune checkpoint blockade followed by subsequent regression and clinical benefit, if the treating clinical team and the patient judge that they have benefitted from therapy, treatment continuation is allowed even if there is disease progression by RECIST v1.1 criteria. However, patients should have confirmed stable disease or better at the time of the following scheduled imaging time-point. **ORR is defined as** the proportion of all randomized subjects whose best overall response (BOR) from baseline is either a CR or PR per RECIST v1.1 criteria. BOR is determined by the best response designation recorded between the date of randomization and the date of objectively documented progression or the date of subsequent anti-cancer therapy, whichever occurs first. For subjects without documented progression or subsequent anticancer therapy, all available response designations will contribute to the BOR determination. For subjects who continue treatment beyond progression, the BOR should be determined based on response designations recorded at the time of the initial RECIST v1.1.

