## 12.2 Secondary End Point

a) *Progression free survival:* It is defined as the time from randomization to the date of the first documented tumor progression (per RECIST v1.1) or death due to anycause. Subjects who die without a reported prior progression will be considered to have progressed on the date of their death. Subjects who did not progress or die will be censored on the date of their last evaluable tumor assessment. Subjects who did not have any on study tumor assessments and did not die will be censored on the date they were randomized. Subjects who started any subsequent anti-cancer therapy without a prior reported progression will be censored at the last evaluable tumor assessment prior to initiation of the subsequent anti-cancer therapy. Progression will be assessed every 6 weeks (from the first on-study radiographic assessment) until disease progression is noted.

b) *Overall survival:* It is defined as the time from randomization to the date of death. A subject who has not died will be censored at last known date alive. OS will be followed continuously while subjects are on the study drug and every 3 months via in-person or phone contact after subjects discontinue the study drug.

c) *Safety and tolerability:* Safety and tolerability objective will be measured by the incidence of adverse events, serious adverse events, deaths, and laboratory abnormalities. Adverse event assessments and laboratory tests are performed at baseline, and continuously throughout the study at the beginning of each subsequent cycle. The safety analysis will be performed in all treated subjects. Descriptive statistics of safety will be presented using

National Cancer Institute (NCI) Common Terminology Criteria for Adverse Events (CTCAE) version 4.0 by treatment arm. All treatment emergent AEs, drug-related AEs, SAEs and drug-related SAEs will be tabulated using worst grade per NCI CTCAE v 4.0 criteria by system organ class and preferred term. On-study lab parameters including hematology, coagulation, chemistry, liver function and renal function will be summarized using worst grade per NCI CTCAE v 4.0 criteria.

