**Evaluation of Best Overall Response**

The best overall response is the best response recorded from the start of the treatment until disease progression/recurrence (taking as reference for progressive disease the smallest measurements recorded since the treatment started). The patient's best response assignment will depend on the achievement of both measurement and confirmation criteria

---

Target Lesions	Non-target Lesions	New Lesions	Overall Response
----------------	--------------------	-------------	------------------

---

---

CR	CR	No	CR
CR	Incomplete response/SD	No	PR
PR	Non-PD	No	PR
SD	Non-PD	No	SD
PD	Any	Yes or No	PD
Any	PD	Yes or No	PD
Any	Any	Yes	PD

---

Note:

Patients with a global deterioration of health status requiring discontinuation of treatment without objective evidence of disease progression at that time should be classified as having “symptomatic deterioration.” Every effort should be made to document the objective progression, even after discontinuation of treatment.

In some circumstances, it may be difficult to distinguish residual disease from normal tissue. When the evaluation of complete response depends on this determination, it is recommended that the residual lesion be investigated (fine needle aspirate/biopsy) before confirming the complete response status.

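### Appendix IV A lets the reference sum for progression restart when treatment is held; this conflicts with the single nadir used elsewhere and can date target-lesion PD later

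*Combined protocol and SAP*

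**What the plan says.** In Appendix IV A, Evaluation of Target Lesions, PD is a rise of at least 20% in the sum of longest diameters, "taking as reference the smallest sum LD recorded from the time treatment was started or from the time treatment was held", or a new lesion. Stable disease is judged "taking as reference the smallest sum LD since the treatment was started or held". Partial response is measured from the baseline sum.

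The Evaluation of Best Overall Response paragraph has one start point: "taking as reference for progressive disease the smallest measurements recorded since the treatment started". Duration of Overall Response and Duration of Stable Disease add a third option, the most recent initiation of treatment. Nothing ranks these wordings.

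Section 12.1 refers to Appendix IV A in its sentence on stopping treatment. Section 12.2 runs PFS from randomization to "the date of the first documented tumor progression (per RECIST v1.1) or death due to anycause". Scans are due "every 8 of weeks i.e after every 2 cycles (4 treatments) of Nivolumab" in Section 12.1, while Section 12.2 says "Progression will be assessed every 6 weeks".

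Holds are part of the design. Section 7.3 delays nivolumab for listed drug-related events in both arms, and Section 7.1 with Table 1 holds THU-Dec in the experimental arm. For nivolumab interruptions, Section 9.3 (Discontinuation Criteria) states: "Tumor assessments should continue as per protocol even if dosing is interrupted or delayed".

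**The concern.** A progression rule needs one reference sum. Here the same appendix offers the nadir since treatment start, a value counted from a hold, and a value counted from the last restart. If a reader resets the reference at a hold, growth between the nadir and the hold is forgiven, and the same scans give a later PD date.

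Nothing in the trial calls for a reset. Scans continue through nivolumab interruptions, so the nadir series need not be broken. The word for a hold also names no drug, although Section 7.3 lets THU-Dec continue while nivolumab is held. If the hold falls between two scans, the text does not say which sum becomes the reference.

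At stake is the PD date used for PFS, and the stopping decision where the team does not judge that the patient is benefiting. THU-Dec holds exist in one arm only, so a distortion need not be equal between arms.

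**Working it through.** The plan gives no figure on this point to reproduce. The check applies the 20% rule to assumed sums under both readings.

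**Direction.** Let m be the smallest sum since treatment start and r the smallest sum since the hold. The window since the hold lies inside the window since start, so r ≥ m and 1.2r ≥ 1.2m. A reset can therefore leave the target-lesion PD date unchanged or move it later, never earlier. If the text means the smallest sum over either window, the reference is m and there is no effect.

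**Worked series.** Assume a nadir of 60 mm, then 70 at the hold, then 80, then 90.
- From the nadir: threshold 1.2 × 60 = 72 mm. The 80 mm scan is PD (80/60 = +33%).
- From the hold: threshold 1.2 × 70 = 84 mm. The 80 mm scan is not PD (80/70 = +14%), and 90 mm is PD (90/70 = +29%). The delay is one scan.
- If the hold falls between the 70 and 80 mm scans, the first sum after the hold is 80. The threshold is 1.2 × 80 = 96 mm, which is 96/60 = +60% over the nadir, and 90 mm is not PD.

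**Effective threshold.** If a scan coincides with the hold and its sum is a fraction h above the nadir, the threshold relative to the true nadir is 1.2(1 + h) − 1. For h = 5%, 10% and 16.7% this is +26%, +32% and +40%.

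**Range of delay.** Assume baseline 100 mm at scan 0 and nadir 60 mm at scan 1.

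| Growth after nadir | Hold at scan | PD scan, single nadir | PD scan, reset | Delay (scans) |
|---|---|---|---|---|
| +10 mm per scan | 1 (nadir) | 3 | 3 | 0 |
| +10 mm per scan | 2 | 3 | 4 | 1 |
| 60, 70, 86 | 2 | 3 | 3 | 0 |
| +25% per scan | 2 | 2 | 2 | 0 |
| +6% per scan | 2, 3, 4 | 5 | 6, 7, 8 | 1, 2, 3 |
| +3 mm per scan | 2, 3, 4 | 5 | 7, 8, 9 | 2, 3, 4 |
| 60, 70, 80, then flat at 80 | 2 | 3 | none | never reached |

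Example for +6% with the hold at scan 4: the nadir threshold is 72 mm. Scan 4 is 60 × 1.06³ = 71.5 and scan 5 is 60 × 1.06⁴ = 75.7, so PD is at scan 5. After the reset the threshold is 1.2 × 71.5 = 85.8 mm. Scan 7 is 60 × 1.06⁶ = 85.1 and scan 8 is 60 × 1.06⁷ = 90.2, so PD is at scan 8.

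One scan is 8 weeks under Section 12.1 or 6 weeks under Section 12.2, so four scans are 32 or 24 weeks.

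**Who is exposed.** Only a patient with a hold after the nadir and before PD, whose first progression event would be target-lesion growth.

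**The case against.** Four arguments weigh against the point.

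1. *The harmless reading.* The smallest sum over both periods is simply the nadir since start. That reading is available. But under it the added words do nothing, and the restart wording in the two duration paragraphs points towards a reset.

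2. *Template residue.* Time to Disease Progression still refers to sunitinib, which is not a study drug. The pointer in Section 12.1 concerns stopping treatment, and PFS rests on the cited guideline. This makes it less likely that the clause would be applied. Even so, the appendix is the only place where the protocol spells out the PD rule.

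3. *Materiality.* Section 3.2 summarizes PFS by Kaplan-Meier and calls the group comparisons primarily exploratory. Sections 3.4 and 12.1 already allow treatment past progression when benefit is judged. This stands and sets the severity.

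4. *Overlapping triggers.* Section 7.3 already delays nivolumab in both arms for most drug-related non-skin events of grade 2 or higher and for many liver test rises. The ALT trigger in Table 1 and the grade 3 non-hematologic trigger in Section 7.1 therefore partly overlap with it. This stands too.

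A reader might also infer more than the documents support:
- *That PD is always one scan late.* That is one series; the table shows zero to four scans, or no target-lesion PD.
- *That the threshold cannot pass 1.2 × 1.2 − 1 = +44% over the nadir.* This needs a scan at the hold and a single hold. The between-scans case gives +60%, and Table 1 foresees recurrent holds.
- *That the seven THU-Dec triggers (six in Table 1 plus non-hematologic toxicity) measure the imbalance between arms.* They overlap with the two-arm delays, and no hold rates are given.
- *That the primary response rate is inflated.* Partial response is measured from baseline, and the best overall response paragraph fixes one nadir. A later PD date would matter only if it kept the Section 12.1 response window open for a patient who had not yet responded and then did. The documents do not show this.

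**Conclusion.** The conflict is real and minor. Appendix IV A contains hold and restart clauses that disagree with its own best overall response paragraph, and PFS in Section 12.2 makes no provision for a reset. Under the reset reading, target-lesion PD is dated the same or later. The delay depends on growth rate and on where the hold falls: zero to four scans in the assumed series, or never reached if the sum plateaus. New-lesion PD, non-target PD and death keep their dates.

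Because THU-Dec holds occur only in the experimental arm, any distortion could lengthen PFS there. That is a possible direction, not a shown bias: the documents give neither hold frequency nor growth rates, so no effect on median PFS or on an error rate can be stated. The conclusion assumes that someone applies the clause as a reset. Under the other reading the effect is nil.

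**What to change.** In Appendix IV A, Evaluation of Target Lesions, delete the hold as an alternative start point in both the PD and the SD definitions. In Duration of Overall Response and Duration of Stable Disease, delete the clauses that restart the reference when treatment was last initiated.

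Add one sentence: the reference for PD and SD is the smallest sum of target-lesion diameters on study, including baseline, with no reset when nivolumab or THU-Dec is held or restarted, and this applies alike to best overall response, PFS and stopping decisions.

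The cost is a few deleted phrases and one added sentence. No scans, visits or patients are added. The sunitinib reference can be removed in the same edit as plain clean-up.
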